All AEs that do not meet any of the criteria for serious should be regarded as non-serious AEs.

Each recorded AE or SAE will be described by its duration (i.e., start and end dates), severity, regulatory seriousness criteria if applicable, suspected relationship to the investigational product (see below), and actions taken.

12.3. Expected adverse event and unexpected adverse event:

Expected adverse events are those that have been previously identified as resulting from administration of the agent. For purposes of this study, an adverse event is considered expected when it is included in the protocol and informed consent document as a potential risk.

An adverse event is considered unexpected when it varies in nature, intensity, or frequency from information provided in the current adverse event list in the protocol and informed consent document as a potential risk.

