
Symptom(s)/ sign(s) of one organ system present
 
Cutaneous
 
Generalized pruritus, urticaria, flushing or sensation of heat or warmth
 
or
 
Angioedema (not laryngeal, tongue or uvular)
 
or
 
Upper respiratory
 
Rhinitis (e.g., sneezing, rhinorrhea, nasal pruritus and/or nasal congestion)
 
or
 
Throat-clearing (itchy throat)
 
or
 
Cough perceived to come from the upper airway, not the lung, larynx, or trachea
 
or
	
Symptom(s)/ sign(s) of more than one organ system present
 
or
 
Lower respiratory
 
Asthma: cough, wheezing, shortness of breath (e.g., less than 40% PEF or FEV1 drop, responding to an inhaled bronchodilator)
 
or
 
Gastrointestinal
 
Abdominal cramps, vomiting, or diarrhea
 
or
 
Other
 
Uterine cramps
 
_____
	
Lower respiratory
 
Asthma (e.g., 40% PEF or FEV1 drop, NOT responding to an inhaled bronchodilator)
 
or
 
Upper respiratory
 
Laryngeal, uvula or tongue edema with or without stridor
	
Lower or Upper respiratory
 
Respiratory failure with or without loss of consciousness
 
or
 
Cardiovascular
 
Hypotension with or without loss of consciousness
	
Death

Conjunctival Conjunctival erythema, pruritus or tearing				
Other Nausea, metallic taste, or headache				

Relationship to Procedure Definitions

Associated: There is a reasonable possibility that the adverse event may have been caused by the test product and/or procedure. This definition applies to those adverse events that are considered definitely, probably or possibly related to the procedure.

1. **Definitely related:** An adverse event that follows a temporal sequence from administration of the test product and/or procedure; follows a known response pattern to the test article and/or procedure; and, when appropriate to the protocol, is confirmed by improvement after stopping the test product (positive re-challenge: and by reappearance of the reaction after repeat exposure [positive re-challenge]); and cannot be reasonably explained by known characteristics of the subject’s clinical state or by other therapies.

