2. **Probably related:** An adverse event that follows a reasonable temporal sequence from administration of the test product and/or procedure; follows a known response pattern to the test product and/or procedure, is confirmed by improvement after re-challenge; and cannot be reasonably explained by the known characteristics of the participant’s clinical state or other therapies.
3. **Possibly related:** An adverse event that follows a reasonable temporal; sequence from administration of the test product and/or procedure and follows a known response pattern to the test product and/or procedure, but could have been produced by the participant’s clinical state or by other therapies.

Not associated: An adverse event for which sufficient information exists to indicate that the etiology is not related to the test product and/or therapy.

Unrelated: An adverse event that does not follow a reasonable temporal sequence after administration of the test product and/or procedure and most likely is explained by the participant’s clinical disease state or by other therapies. In addition, a negative re-challenge to the test article and/or procedure would support an unrelated relationship.

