12.6. Safety Reporting Requirements for IND Holders

Additional reporting requirements for the FDA in accordance with the guidance set forth in 21 CFR 212.32 are required. Sponsor-investigators of studies conducted under an IND will comply with the safety reporting requirements outlined below.

12.6.1. Expedited IND Safety Reports:

Seven calendar-day telephone or fax report: The Sponsor-Investigator is required to notify the FDA of any fatal or life-threatening adverse event that is unexpected and assessed by the investigator to be possibly related to the use of peanut OIT. An unexpected adverse event is one that is not already described in the consent form. Such reports are to be telephoned or faxed to the FDA within 7 calendar days of first learning of the event. Each telephone call or fax transmission (see fax number below) should be directed to the FDA new drug review division in the Center for Drug Evaluation and Research or in the product review division for the Center for Biologics Evaluation and Research, whichever is responsible for the review of the IND.

12.6.2. Fifteen calendar-day written report:

The Sponsor-Investigator is also required to notify the FDA and all participating investigators, in a written IND Safety Report, of any serious, unexpected AE that is

considered possibly related to the use of peanut OIT.

12.6.3. **Written IND Safety Reports:**

Will include an Analysis of Similar Events in accordance with regulation 21 CFR 312.32. All safety reports previously filed with the IND concerning similar events should be analyzed. The new report should contain comments on the significance of the new event in light of the previous, similar reports.

Written IND safety reports with Analysis of Similar Events are to be submitted to the FDA within 15 calendar days of first learning of the event. The FDA prefers these reports on a MedWatch 3500a Form but alternative formats are acceptable (e.g. summary letter). MedWatch Forms along with submission instructions can be found at the following FDA website:

<http://www.fda.gov/Safety/MedWatch/HowToReport/DownloadForms/default.htm>.

FDA fax number for IND Safety Reports: [name]

12.6.4. **IND Annual Reports**

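### Every related category in 12.4 requires a known response pattern, so a well-timed reaction that is new in nature has no causality category and, read literally, misses the possibly-related trigger in 12.6

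*Combined protocol and SAP*

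**What the plan says.** **Causality (12.4, Relationship to Procedure Definitions).** *Associated* is the umbrella term: "There is a reasonable possibility that the adverse event may have been caused by the test product and/or procedure". The next sentence ties it to events judged definitely, probably or possibly related. The lowest of these, *possibly related*, needs a reasonable temporal sequence "and follows a known response pattern to the test product and/or procedure, but could have been produced by" something else, namely disease or other treatment. On the other side, *Not associated* needs enough information to show that the cause is not the product. *Unrelated* is "An adverse event that does not follow a reasonable temporal sequence after administration of the test product and/or procedure" and is most likely explained by disease or other treatment.

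**Expectedness (12.3 and 12.6.1).** Section 12.3 states: "An adverse event is considered unexpected when it varies in nature, intensity, or frequency from information provided in the current adverse event list"; the list meant is the one carried by the protocol and the consent document. Section 12.6.1 defines unexpected more simply, as not described in the consent form.

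**Expedited reports (12.6.1, 12.6.2).** The 7-day report covers "any fatal or life-threatening adverse event that is unexpected and assessed by the investigator to be possibly related to the use of peanut OIT". The 15-day report covers serious, unexpected events considered possibly related.

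**Other uses of relatedness.** Section 12.5 follows serious and treatment-related events to resolution, but other events ongoing at study end for only 30 days after the last dose. In the stopping rules (section 6, Criteria for Premature Termination of the Study), the death rule and the Grade 4 anaphylaxis rule both refer to events related to OIT dosing.

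**The concern.** A causality scale should be able to record the first occurrence of a reaction nobody has seen before. Here the condition that the event resemble something already known appears in every related tier, including the one meant to catch uncertain cases. That conflicts with the umbrella standard in the same section, which asks only whether causation is reasonably possible.

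The definitions carry more weight than usual in this trial. The Background names safety as the primary outcome, there is no placebo arm, and target enrolment is 15. Without a comparison group, a new toxicity can be recognised only by judging individual events. The Principal Investigator makes that judgement. If the scale has no place for a new kind of reaction, the protocol's expedited reporting and extended follow-up depend on the investigator setting the written definitions aside.

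**Working it through.** No figure in the plan is in question, so the check is to apply the written conditions to different kinds of event.

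**Step 1. Conditions for each category in 12.4.**

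| Category | Timing | Known pattern | Other condition |
|---|---|---|---|
| Definitely related | required | required: "follows a known response pattern to the test article and/or procedure" | no other reasonable explanation; where appropriate, confirmation on stopping and on re-exposure |
| Probably related | required | required: "follows a known response pattern to the test product and/or procedure, is confirmed by improvement after re-challenge" | no other reasonable explanation |
| Possibly related | required | required (joined to timing by *and*) | another cause could explain it |
| Not associated | not stated | not stated | positive information that the product is not the cause |
| Unrelated | must be absent | not stated | most likely explained by disease or other therapy |

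**Step 2. A reaction new in nature: plausible timing, no known pattern, no evidence against causation.** It fails all three related tiers on the pattern condition. It fails *Unrelated* because the timing is reasonable, and *Not associated* because no contrary information exists. It has no category. It does satisfy the reasonable-possibility sentence of *Associated*, but that term is said to apply to the three tiers the event has just failed, so it offers no fourth route.

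**Step 3. Consequences for that event on a literal reading.**
- 12.6.1 and 12.6.2: serious and unexpected, but not possibly related, so neither expedited condition is met.
- 12.5: if non-serious and ongoing at study end, it is not treatment related, so it gets 30 days rather than follow-up to resolution.
- Death stopping rule: whether a death of this kind counts as related is left open.

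**Step 4. Events the gap does not reach.**
- Known pattern, but unexpected in intensity or frequency (12.3): can be both unexpected and possibly related, so the report is triggered if the seriousness condition is met.
- Known pattern, but not described in the consent form (12.6.1): same result.
- Grade 4 anaphylaxis: the protocol itself lists anaphylaxis as a recognised risk of OIT, so the pattern condition is met and the rule works as written.

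**The case against.** The strongest reply is that *possibly related* in 12.6 cannot mean the third tier alone, because events judged probably or definitely related would then escape reporting. It must mean at least possibly related, which is in effect *Associated*. That reading is sensible. It does not close the gap by itself, because *Associated* is tied to three tiers that all carry the pattern condition. It would do so only if the reasonable-possibility sentence governed alone, and 12.4 does not say that.

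A second reply is that other duties do not depend on relatedness. Section 12.5 has all adverse events recorded, serious ones sent to the IRB, and all reported to the FDA on its own terms. Section 12.2 requires deaths to be reported whether or not they are related. This stands as a partial backstop. But 12.6 is where the protocol sets out the 7-day and 15-day conditions, and those use the affected term.

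A reader might go further and infer four things that the documents do not support:
- *Expedited reports for unexpected events can never be triggered.* Step 4 shows that they can.
- *Every event unexpected in nature is shut out.* Known pattern is not defined and is not limited to the listed risks. Table 8 grades uterine cramps as an immunotherapy reaction, for example, although the section 7 risk list omits them. Such an event can be unlisted in section 7 and still follow a known pattern. The consent pages are not available for checking.
- *The Grade 4 stopping rule is disabled.* It counts anaphylaxis, a known pattern. The rules on epinephrine use and eosinophilic esophagitis do not use the 12.4 categories.
- *The primary safety result is distorted.* Section 9.2.1 uses daily symptoms and challenge outcomes without filtering by relatedness, and no safety table by causality category is specified.

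**Conclusion.** The point holds in a limited form. For a reaction that is new in nature, with plausible timing and no evidence against causation, 12.4 provides no category and contradicts its own umbrella standard. Literal application leaves the expedited-report condition unmet, shortens follow-up for a non-serious event, and makes the death stopping rule uncertain.

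The size is a class of events, not a rate. The documents give no basis for estimating how many such reactions would occur among 15 subjects, and the number may be small or zero. The class is nevertheless one that expedited reporting most needs to catch.

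The conclusion rests on two assumptions. The first is that a known response pattern means a type of reaction already recognised with peanut exposure or OIT; a looser reading narrows the gap. The second is that relatedness in 12.5, 12.6 and the stopping rules is judged by the 12.4 definitions. Those sections do not cite 12.4, but it is the only place where the protocol defines relatedness.

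**What to change.** In 12.4, define *possibly related* as a reasonable temporal sequence together with a reasonable possibility of causation, where the criteria for probably or definitely related are not met, and with no known-pattern requirement. The pattern condition can stay in the two higher tiers.

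In 12.6.1 and 12.6.2, state that the causality condition is met by any event classed as *Associated*, that is, at least possibly related. It would also help to reconcile the two definitions of unexpected in 12.3 and 12.6.1, and to state whether relatedness in 12.5 and in the stopping rules is judged by the 12.4 definitions.

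This needs no new data, procedure or sample size. The cost is that somewhat more events will be classed as related. With one dose every day, an intercurrent illness will often begin soon after a dose, so timing alone discriminates poorly and some such illnesses will be included. Keeping reasonable possibility as a separate requirement limits this but does not remove it.

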12.5. Adverse Event Reporting

All adverse events, regardless of perceived relationship to study treatment, will be reported and recorded on the appropriate Case Report Forms (CFR Title 21, 312.32). New AEs and SAEs that are ongoing at the end of the study will be followed for 30 days from the patient's receipt of the last dose of protocol therapy, unless they have resolved earlier. SAEs and treatment related AEs ongoing at the end of study will be followed until resolution.

The AE description will include the nature of the experience, the date of onset, the resolution date, the severity of each sign or symptom reported using grade 1 to 5, the seriousness of the event, the potential relationship to study treatment, the course of action taken, and the outcome of the experience.

Serious adverse events are to be reported to the institutional review board (IRB) according to each board's reporting requirements and required time frame.

The Principal Investigator will be responsible for reporting all adverse events to the FDA as per their reporting requirements and time frame.

12.6. Safety Reporting Requirements for IND Holders

Additional reporting requirements for the FDA in accordance with the guidance set forth in 21 CFR 212.32 are required. Sponsor-investigators of studies conducted under an IND will comply with the safety reporting requirements outlined below.

12.6.1. Expedited IND Safety Reports:

Seven calendar-day telephone or fax report: The Sponsor-Investigator is required to notify the FDA of any fatal or life-threatening adverse event that is unexpected and assessed by the investigator to be possibly related to the use of peanut OIT. An unexpected adverse event is one that is not already described in the consent form. Such reports are to be telephoned or faxed to the FDA within 7 calendar days of first learning of the event. Each telephone call or fax transmission (see fax number below) should be directed to the FDA new drug review division in the Center for Drug Evaluation and Research or in the product review division for the Center for Biologics Evaluation and Research, whichever is responsible for the review of the IND.

12.6.2. Fifteen calendar-day written report:

The Sponsor-Investigator is also required to notify the FDA and all participating investigators, in a written IND Safety Report, of any serious, unexpected AE that is

considered possibly related to the use of peanut OIT.

12.6.3. **Written IND Safety Reports:**

Will include an Analysis of Similar Events in accordance with regulation 21 CFR 312.32. All safety reports previously filed with the IND concerning similar events should be analyzed. The new report should contain comments on the significance of the new event in light of the previous, similar reports.

Written IND safety reports with Analysis of Similar Events are to be submitted to the FDA within 15 calendar days of first learning of the event. The FDA prefers these reports on a MedWatch 3500a Form but alternative formats are acceptable (e.g. summary letter). MedWatch Forms along with submission instructions can be found at the following FDA website:

<http://www.fda.gov/Safety/MedWatch/HowToReport/DownloadForms/default.htm>.

FDA fax number for IND Safety Reports: [name]

12.6.4. **IND Annual Reports**

In accordance with the regulation 21 CFR 312.32, the Sponsor-Investigator shall within 60 days of the anniversary date that the IND went into effect submit a brief report of the progress of the investigation. Please refer to Code of Federal Regulations, 21 CFR 312.32 for a list of the elements required for the annual report.

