⁷Peanut Equivalent Dose

⁸Buccal mucosa will be performed only once after 6 months maintenance visit has been reached for HLA typing to allow for tetramer analysis

7. POTENTIAL RISKS AND DISCOMFORTS:

Peanut oral immunotherapy may cause some, all or none of the side-effects listed below.

The buildup and daily maintenance doses of OIT may cause allergic symptoms. The likelihood of a subject experiencing any allergic symptoms will be lessened by initiating dosing at extremely small amounts of the peanut protein.

Symptoms often seen with therapy and during the food challenges:

Likely (more than 20% of subjects)
 
• Rare bursts of sneezing or nasal itching• Occasional sniffing• Mild congestion• Occasional scratching• Mild nausea or abdominal pain (e.g. no change in activity level) (~43% of subjects on initial escalation day)• Moderate nausea or abdominal pain (e.g. noticeable decrease in activity level) (~29% of subjects on initial escalation day)• 1 episode of vomiting or diarrhea• Throat clearing• Occasional cough• Mild urticaria (less than 3 hives)• Mild rash (few areas of faint redness)

Unlikely (2 – 20% of subjects)
 
• Frequent sniffing• Hoarseness or a frequent dry cough• 2 to 3 episodes of vomiting or diarrhea• Itching of more than 50% of the body• Skin redness covering more than 50% of the body• Hives covering more than 50% of the body• Continuous scratching for more than 2 minutes• Wheezing

Serious but Rare (less than 2% of subjects)
 
A potential risk associated with both the desensitization procedure and food challenge is the risk of a severe allergic reaction, called anaphylaxis, which may occur in <2% of patients. Symptoms of anaphylaxis may include those listed above (itchy rash, hives, facial swelling, wheezing, cough, shortness of breath, vomiting, diarrhea), and in severe cases low blood pressure, loss of consciousness, and, rarely, death. Medication, personnel, and equipment are immediately available in the event of an anaphylactic reaction.
 
The potential discomforts with the desensitization procedure or food challenge are no more

than when eating the suspected food in the past. Symptoms usually are short-lived (less than 2 hours). To minimize the risk of reaction, small amounts of the food suspected to cause a reaction will be given at the start of the desensitization procedure and food challenge.

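### Sections 12.3 and 12.6.1 define an unexpected adverse event differently, and the narrower definition sits in the 7-day IND reporting rule

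*Combined protocol and SAP*

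**What the plan says.** Section 12.3 defines both terms. On the expected side, "an adverse event is considered expected when it is included in the protocol and informed consent document as a potential risk". On the unexpected side, "An adverse event is considered unexpected when it varies in nature, intensity, or frequency from information provided in the current adverse event list", the list being the one held in the protocol and the consent document.

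Section 12.6.1 sets the 7-day telephone or fax report. Its trigger is "any fatal or life-threatening adverse event that is unexpected and assessed by the investigator to be possibly related to the use of peanut OIT", and the paragraph then supplies its own definition: "An unexpected adverse event is one that is not already described in the consent form".

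Section 12.6.2 sets the 15-day written report. It applies to notification "of any serious, unexpected AE that is" judged possibly related to peanut OIT, and gives no definition of the term.

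Section 7, under its serious but rare risks, names anaphylaxis, "which may occur in <2% of patients", with features that include "in severe cases low blood pressure, loss of consciousness, and, rarely, death". Section 12.1 also lists hypotension and circulatory collapse under anaphylaxis.

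**The concern.** Both expedited reports depend on the word *unexpected*, and the protocol does not say which of its two definitions controls. The one placed inside the 7-day rule is the one a sponsor-investigator working through that rule is likely to apply. It drops the comparison of nature, intensity and frequency and asks only whether the event is already described.

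This affects the trial's main named hazard. Section 1 makes safety the primary outcome, the participants are children, and severe allergic reaction is the principal serious risk in Section 7. A life-threatening reaction, or a cluster of reactions above the listed rate, could be classed as unexpected under 12.3 and as expected under 12.6.1. Whether FDA hears within 7 days would then depend on which paragraph was consulted. One party, the sponsor-investigator, judges relatedness and applies the expectedness test.

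**Working it through.** The plan states no figure on this point, so the check is a comparison of the passages, followed by one illustrative calculation.

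**The two definitions applied to the same event**

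| Event, possibly related to peanut OIT | Section 12.3 | Section 12.6.1, read literally |
|---|---|---|
| Of a type not in the consent form | Unexpected | Unexpected |
| Described in the consent form, at the listed intensity and frequency | Expected | Expected |
| Described, but more intense than listed | Unexpected on the variation test | Not unexpected |
| Described, but more frequent than listed | Unexpected on the variation test | Not unexpected |

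The definitions part in the last two rows. There, 12.3 also has an internal tension: its sentence on expected events turns on inclusion in the protocol and consent document, and does not say that the variation test overrides inclusion. Deleting the 12.6.1 sentence alone would therefore leave part of the problem in 12.3.

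**Which events fall in those rows**

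This depends on the consent form, which is not among the available documents. The assumption is that it carries the Section 7 risks. That is reasonable, because 12.3 treats the protocol and consent document as holding the adverse event list together. On that assumption, hypotension, loss of consciousness and death in anaphylaxis are all already described for the purposes of 12.6.1.

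**What the frequency limb could mean with 15 children**

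Inputs: n = 15 (target enrollment, Section 1) and listed frequency of anaphylaxis below 2% of patients (Section 7). The calculation takes p = 0.02, the upper bound of the listing, as an assumed true rate and treats children as independent.

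- Observed proportions: 1/15 = 6.7%; 2/15 = 13.3%.
- P(0) = 0.98^15 = 0.7386.
- P(1) = 15 × 0.02 × 0.98^14 = 0.2261.
- P(at least 1) = 1 − 0.7386 = 0.26.
- P(at least 2) = 1 − 0.7386 − 0.2261 = 0.035.

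One case is compatible with the listed rate, although its observed proportion exceeds 2%. Two or more would be uncommon at that rate and could reasonably be judged unexpected in frequency under 12.3. Under 12.6.1 the count makes no difference. Section 12.3 sets no numerical threshold, so this is an illustration and not a rule taken from the protocol.

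**The case against.** The strongest reply is that other provisions remain in force.

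- Section 12.5 makes the principal investigator responsible for reporting all adverse events to FDA on FDA's own requirements and timing, with no expectedness filter. Section 12.6 describes its requirements as additional, so it does not cap 12.5.
- Nothing in 12.6.1 says that it displaces 12.3.
- Serious adverse events go to the IRB whether or not they are expected (12.5).
- A single related death stops the study for review by the principal investigator and the IRB (6.10, stopping rules). A Grade 4 reaction ends that child's participation under the individual stopping rules (6.11).
- The Data and Safety Review Committee monitors toxicities and adverse events (8.2).

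All of this stands, and it limits the consequence. It does not settle which definition applies to the 7-day report. Section 12.5 states no number of days, and whether its reference to FDA timing closes the gap depends on regulatory text outside the documents. No view is taken on that here.

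A reader might infer more than the documents support:

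- *That a fatal or hypotensive reaction would never be reported on an expedited basis.* The consent form is unseen, and 12.3 and 12.5 still apply. The literal wording permits non-reporting under 12.6.1; it does not require it.
- *That the 15-day report is excluded in the same way.* The narrow sentence sits in the 7-day paragraph. Section 12.6.2 has no definition, so 12.3 could govern it.
- *That the expedited reports are the only timed reports leaving the institution.* Section 12.6.4 also requires an annual IND report within 60 days of the anniversary date, although that is much slower.
- *That the listed rate below 2% is a benchmark for Grade 4 reactions.* It is given for anaphylaxis generally, across desensitization and food challenge. No Grade 4 rate is listed.

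**Conclusion.** The inconsistency is real and visible in the text. Sections 12.3 and 12.6.1 give different answers for any event that is described in the consent form but departs from its listing in intensity or frequency, and 12.6.2 leaves the term undefined. If the consent form repeats Section 7, a possibly related fatal or life-threatening allergic reaction need not trigger the 7-day report on the literal wording of 12.6.1.

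The size is best stated as ambiguity over a small number of important reports. No endpoint or analysis changes. The probabilities shown rest on an assumed 2% rate and 15 independent participants. They show only that a cluster which 12.3 could catch would pass 12.6.1 unnoticed.

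A reader might also want a rule that every related fatal or Grade 4 event is expedited whether or not it is listed. No passage requires that, so it is a preference and not a correction. Equally, applying 12.3 would not make every listed death unexpected: that would still turn on comparison with the listing. The supportable conclusion is that the definitions must be reconciled, and that the variation test in 12.3 should govern because it responds to intensity and frequency.

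**What to change.** Make three wording changes in one amendment.

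1. In 12.6.1, delete the sentence "An unexpected adverse event is one that is not already described in the consent form".
2. In 12.6, state that for both the 7-day and the 15-day report the term has the meaning given in 12.3, that is, a departure in nature, intensity or frequency from the listed risks.
3. In 12.3, state that inclusion in the protocol and consent document does not by itself make an event expected if its intensity or frequency differs from the listing.

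While drafting, check the consent form against Section 7, so that the list on which the definition relies is the same in both places.

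The cost is a few lines of text and at most a few additional expedited reports in a 15-subject study. No procedure, visit or analysis changes.
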